### 3.5.3.5 Exploratory Analyses

Analyses of exploratory endpoints will be based on the FAS where at least one baseline and one post-baseline assessment are available. Missing data will not be imputed. Analyses will focus on comparing the post-baseline values with the baseline value.

#### **Exploratory Endpoints**

Exploratory analyses based on standard RECIST 1.1, Choi Criteria, and Volumetric Criteria will not be performed. Due to specific radiographic image requirements for an evaluation and comparison by the independent radiological reviewer, the number of scans collected in the trial meeting these requirements are limited and will not be able to provide a meaningful comparison with the trial's primary and secondary efficacy endpoints.

## Biomarkers

02 November, 2021

**BRACHY-CHOR-001** 

Samples for PBMC and serum will be collected at Screening/Baseline, Day 28, 2 weeks from end of radiation, and 6 weeks from end of radiation. Measurements from samples taken prior to first trial vaccination are referred to as baseline values.

Results from two ELISPOT tests will be analyzed: single peptide Brachyury-specific T cells and peptide pool Brachyury-specific T cells. Summary tables will be generated for the results for each test by visit and will also be listed. Along with observed results, ratio to baseline results will also be presented in the summary table for post-baseline visits. Geometric mean will be calculated by taking the antilogarithm of the mean of the log10 transformations. The detection limit (DL) is defined as 10. Results below the DL will be given a value of ½ of DL for the purpose of calculations. Descriptive statistics will be derived for all visits including number of observations, geometric mean, with 95% CI (derived based on the antilogarithm of the 95% CI of the log10 transformations constructed using the t-distribution), median, minimum and maximum. Geometric mean with 95% CI by visit will also be presented in a figure.

Additionally, ELISPOT results for each test will be summarized by best overall tumor response per mRECIST by visit to explore the correlation between tumor response and immune response. Descriptive statistics will be derived for all visits including number of observations, geometric mean, with 95% CI (derived based on the antilogarithm of the 95% CI of the log10 transformations constructed using the t-distribution).

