### 10.4.5.3 Exploratory Analyses

Analyses of biomarker exploratory endpoints will be based on the FAS where at least one post-baseline and the baseline assessment is available. Missing data will not be imputed. Analyses will focus on comparing the post-baseline value with the baseline value. Correlation between tumor response and immune responses will be explored.

Continuous data will be summarized via mean, standard deviation, median, minimum, and maximum by visit where samples are collected per trial schedule. 95% confidence intervals of the mean will be computed. Log transformation of the data may be performed (e.g., ANA titer), and therefore the geometric mean and the 95% confidence interval will be summarized instead.

For response rate and other categorical data, number and percentage will be summarized.

For additional analyses of PFS, the following methods will be used:

- PFS by the Choi response criteria based on target lesion(s): (Choi, 2007) During the course of immunotherapy, changes in tumor dimensions do not necessarily reflect tumor response. In the Choi (Choi, 2007) response criteria, progressive disease is defined as  $\geq 10\%$  increase in sum of longest diameters of lesions; does not meet the criteria for partial response by virtue of tumor attenuation, new intratumoral nodules, or an increase in the size of the existing intratumoral modules.
- PFS based on target lesion(s) by volumetric segmentation (Fenerty et al., 2016)
- PFS based on all lesions by standard RECIST 1.1

ORR analysis using standard RECIST 1.1 based on all lesions, using the Choi (Choi, 2007) and volumetric criteria (Fenerty et al., 2016) based on target lesion(s) per external radiological review will be performed similar to the primary analysis.

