#### 3 Statistical Methods

## 3.1 Planned Sample Size

The null hypothesis that the true ORR anytime within 12 months after completion of radiation is 5% will be tested based on a one-sided alternative. In the first stage, 10 subjects will be accrued. If there are 0 responders in these 10 subjects, the trial will be terminated. If there is at least 1 responder in these 10 subjects, 19 additional subjects will be accrued for a total of 29 subjects. The null hypothesis will be rejected if 4 or more responses are observed in 29 subjects. This design retains a one-sided type I error rate of  $\leq 0.05$  and achieves 80% power when the true response rate is 20%.

The optimal design minimizes the expected sample size under the null hypothesis while satisfying the type I error and power constraint. With the above design, the probability of early termination is 60% and the expected sample size is 17.6 when the true response rate is 5% (under the null hypothesis).

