**BRACHY-CHOR-001** 

The 90% Wilson score confidence intervals will be calculated. The duration of response and tumor measurements will only be provided in subject-level listings.

Percent change from Baseline in target lesion by visits will be plotted for the EAS by different subgroups: best OR, current radiation dose group categories (≤ median current radiation dose in Gray and > median current radiation dose in Gray), baseline disease location, and therapy type (proton therapy and other therapy).

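### The SAP explores the tumor/immune correlation only through ELISPOT means within best-response categories and gives no measure of association, although percent change in the target lesion is already derived

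*SAP*

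**What the plan says.** Protocol 10.4.5.3 makes the commitment in general terms: "Correlation between tumor response and immune responses will be explored". It names no method.

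The SAP implements it in the Biomarkers part of 3.5.3.5, with ELISPOT as the immune measure: "ELISPOT results for each test will be summarized by best overall tumor response per mRECIST by visit to explore the correlation between tumor response". Within each response category and visit the output is "number of observations, geometric mean, with 95% CI", computed on the log10 scale. No coefficient, model, test or scatter plot is named. The same subsection derives the ELISPOT ratio to baseline for the overall visit table, but does not say that the by-response table will use it. Results below the detection limit of 10 are set to half that limit.

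The continuous tumor measure appears in SAP 3.5.3.3.1: "Percent change from Baseline in target lesion by visits will be plotted for the EAS by different subgroups". The grouping factors are best response, radiation dose group, disease location and therapy type. ELISPOT is not among them.

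The populations differ. The tumor plots use the evaluable set (EAS). For the biomarkers, "Analyses of exploratory endpoints will be based on the FAS where at least one baseline and one post-baseline assessment are available".

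**The concern.** Tumor change is a graded quantity, and the response categories cut it at fixed thresholds. Those categories are needed for the response-rate test, but nothing in the plan requires them for this question. Protocol 2.3 itself reports that after high-dose radiotherapy alone no patient had reached an objective response at 12 months. Graded shrinkage below the response threshold may therefore be common, and a category table cannot show it.

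Protocol 2.5.8 rests the regimen on radiation making chordoma cells susceptible to Brachyury-specific T cells. All subjects in this single-arm trial are irradiated and vaccinated, and the by-response table is the only planned analysis that relates the T-cell response to tumor shrinkage. SAP 3.5.3.5 also drops the Choi and volumetric analyses, so no other tumor measure fills the gap. At stake is how much the trial can say about its own rationale, not whether it succeeds.

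**Working it through.** **1. The plan's own figure.** SAP 3.1 gives 10 subjects in stage 1 (continue on at least 1 response), then "19 additional subjects will be accrued for a total of 29 subjects", with rejection at 4 or more responses. Exact two-stage binomial:
- At 5%: probability of early stopping 0.95^10 = 0.599; expected N = 10 + 19 × (1 − 0.599) = 17.6; type I error 0.047.
- At 20%: power 0.801.

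All stated figures reproduce. The documents state no power or precision for the tumor/immune correlation.

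**2. Size of the responder cell, N = 29.**
- At 20%: expected responders 0.20 × 29 = 5.8. P(fewer than 2) = 0.8^29 + 29 × 0.2 × 0.8^28 = 0.013.
- At 5%: expected 0.05 × 29 = 1.45. P(fewer than 2) = 0.95^29 + 29 × 0.05 × 0.95^28 = 0.226 + 0.345 = 0.571. A category with fewer than 2 subjects has no interval.
- The 57% ignores the stage 1 rule. Among trials that pass stage 1 at a true 5%, it is 10 × 0.05 × 0.95^28 / (1 − 0.95^10) = 0.119 / 0.401 = 0.30.

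**3. Information kept by a responder split.** For a normal variable cut so that 20% fall above the cut, the share kept is φ(z)² / (p q) = 0.28² / (0.2 × 0.8) = 0.49, about half.

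**4. Power under assumed scenarios.** Assumptions, none given in the documents: log10 ELISPOT and tumor change bivariate normal, N = 29 with complete data, 20% CR/PR, 60% SD, 20% PD, two-sided 5%. Simulated power:

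| Analysis | rho 0.4 | rho 0.5 |
|---|---|---|
| Spearman, full scale | 53% | 76% |
| Ordered trend over three categories | 46% | 66% |
| Responder vs non-responder t-test | 31% | 47% |

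The SAP plans none of these three tests. The full-scale gain is 7 to 10 points over the ordered trend and 22 to 29 points over the responder split.

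Analytic check for the full scale: d = atanh(rho) × √((N − 3)/1.06), power = Φ(d − 1.96) + Φ(−d − 1.96). At 0.3, 0.4 and 0.5, d = 1.53, 2.10 and 2.72, giving 33%, 55% and 78%. This is close to the simulation.

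**5. Sensitivity at rho 0.4.** Full-scale Spearman power falls to about 47% if half the ELISPOT values sit at the half-limit floor, and to about 38% if only 20 subjects have usable data. The documents give neither the share below the limit nor the number with ELISPOT results.

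**6. Precision of a coefficient.** For an observed 0.4 at N = 29: 0.424 ± 1.96 × √(1.06/26) = 0.424 ± 0.396 on the Fisher scale, which back-transforms to about 0.03 to 0.67. The interval is wide, and it shows that openly.

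**The case against.** The protocol promises only exploration, and a descriptive table by response is one way to explore. SAP 3.5.3.4.2 treats pain and tumor response similarly. This stands: the SAP breaks no commitment.

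A reader might infer that the planned table would usually miss a real moderate association. The documents do not support that, because the SAP sets no rule for declaring one. If separation of the responder and non-responder 95% intervals is taken as the rule, the chance is about 11% at rho 0.4 and 19% at 0.5. But that rule is not in the SAP, and its false-positive rate is only about 1%, so it cannot fairly be set against a 5% test. Against an ordered trend the loss is modest, and at rho 0.5 a categorical trend would detect the association about two times in three. Sample size is the larger limit.

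The remedy also has limits. It adds unadjusted coefficients, needs a newly defined variable and a common population, and meets ties at the detection floor. Radiation dose varies between subjects and could affect both measures, so a pooled coefficient describes association and does not isolate a mechanism. The SAP itself counts a decrease of less than 5 mm as no shrinkage, so small changes may be noise.

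Finally, ELISPOT results will be listed, lesion sizes will appear in subject-level listings, and the SAP allows additional analyses if labelled unplanned. Little is lost for good. What is lost by waiting is prespecification.

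**Conclusion.** The point holds as a gap in method. The only planned look at the tumor/immune correlation yields no measure of association and sets aside a continuous measure that the SAP already derives. Under the stated assumptions the full scale gains about 7 to 10 points of power over the best categorical comparator and 22 to 29 over a responder split, for true correlations of 0.4 to 0.5. At 0.3 it has only about 33% power, so it does not rescue weak associations. The correlation values, category shares and complete data are assumptions, and missing ELISPOT results or values at the floor would lower the power.

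The stronger conclusion, that a moderate association would usually go undetected because of the categories, needs a detection rule that the SAP does not contain. The analysis is exploratory and bears on no primary, secondary, safety or go/no-go decision. It is a cheap improvement, not a flaw in the trial's inference.

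**What to change.** In the Biomarkers part of SAP 3.5.3.5 add, for each of the two ELISPOT tests:
- A scatter plot and a Spearman correlation with 95% CI between the log10 ratio to baseline (Day 28, End Radiation + 2 weeks, End Radiation + 6 weeks) and the best percent change from baseline in the target-lesion sum within 12 months after radiation.
- A definition of best percent change, including which scans count.
- A common population: subjects with baseline and post-baseline values for both measures, with the number shown.
- A distinct plotting symbol for ELISPOT values set to half the detection limit.
- A statement that the results are exploratory and unadjusted for multiplicity.

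Keep the best-response table as descriptive support.

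Cost: a short SAP paragraph, one new derived variable, and 2 tests × 3 visits = 6 extra coefficients. If the six were independent and no association existed, the chance of at least one nominal 5% result would be 1 − 0.95^6 = 26%, so emphasis should fall on estimates and intervals. No new data are needed.

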## 3.5.4 Subject Disposition

All subjects screened and having signed informed consent will be accounted for. A summary table specifying the number and percentage of subjects ineligible following screening (and reasons), meeting all eligibility criteria, treated, completing the treatment period (pre-radiation vaccination period, radiation therapy period, post-radiation vaccination periods), discontinuing trial treatment early (and reasons), and not completing the post-treatment follow-up visit (and reasons) will be generated.

A listing will present all enrolled subjects, flag for analysis sets, date of completion or discontinuation, reason for discontinuation, last trial day (weeks), and last post-radiation therapy day (weeks). All subjects not eligible for the trial will be listed, including the reason why they were not eligible.

Subjects who are excluded from the EAS, flag for analysis sets (FAS and EAS) and reasons for exclusion will be listed. Other protocol deviations will also be provided in a subject level listing.

## 3.5.5 Demographics and Baseline Characteristics

#### 3.5.5.1 Demographics and Baseline Characteristics Variables

#### **Demographics**

- Age

BRACHY-CHOR-001

- Age Group (12 to <18, 18+)
- Sex (Male, Female)
- Race (White, Black or African American, Asian, Native American or Alaska Native, Native Hawaiian or Other Pacific Islander, Other)
- Race Group (White, Other)
- Ethnicity (Hispanic or Latino, Not Hispanic or Latino)

#### **Baseline Characteristics**

- Height (cm)
- Weight (kg)
- Body Mass Index (BMI; kg/m^2)
- HIV antibody (positive, negative)
- Hepatitis B surface antigen (positive, negative)
- Hepatitis C virus (positive, negative)

## Baseline Disease Characteristics

- Eastern Cooperative Oncology Group (ECOG) Status (0, 1, 2)
- Disease duration at screening (years; date of diagnosis to date of informed consent)
- Original diagnosis
- Histological classification (classical, chondroid)
- Primary tumor site (clival, mobile spine, sacral)
- Disease status at diagnosis (localized, locally advanced, metastatic)
- Current disease status (localized, locally advanced, metastatic)
- Curative intervention (yes, no), duration of primary curative intervention, disease-free intervals, and time from recurrence after a disease-free interval, if applicable.
- Site of metastasis, if applicable

#### 12-Lead Electrocardiogram (ECG) at Screening

- Investigator's overall interpretation (normal, abnormal)
- Investigator rated clinical significance (clinically significant, not clinically significant)

#### 3.5.5.2 Demographics and Baseline Characteristics Analyses

Demographics and baseline characteristics will be summarized based on the FAS. An additional summary table will be generated based on the EAS.

Age is recorded at the time of screening and will be presented using continuous statistics.

BMI will be calculated as:

 $BMI = weight (kg) / [height (m)]^2$ 

02 November, 2021

BRACHY-CHOR-001

Baseline disease characteristics will be summarized using continuous statistics or percentages and frequencies, as appropriate.

Disease duration at baseline in years will be calculated as:

If applicable, time from recurrence after a disease-free interval to first trial treatment in years will be calculated as

```
(Date of First Treatment - Date of Recurrence + 1) / 365.25
```

Note if either the initial diagnosis date or recurrence date are partial, they will be imputed based on the missing date rules in Section 3.4.1.

If dates are complete, duration of curative intervention and disease-free intervals will be calculated and will be included in subject-level listings only. Missing or partial dates will not be imputed.

Duration of curative intervention in months will be calculated as:

```
(End Date of Primary Curative Intervention - Start Date of Primary Curative Intervention + 1) / 30.4
```

Disease-free interval in months will be calculated as:

```
(Date of Recurrence - End Date of Primary Curative Intervention + 1) / 30.4
```

In addition, sites of metastasis will be included only in subject-level listings. Screening ECGs will also be listed.

## 3.5.5.3 Medical History

Relevant medical history will be summarized for the purpose of characterizing the trial population based on the FAS. Medical history terms will be coded by SOC and PT to the MedDRA version 21.0 or higher.

For medical histories, summaries by SOC and PT will count a subject once for each SOC, and once for each PT within an SOC. SOCs will be displayed in the order of descending frequency, and PTs will be displayed by descending frequency within SOC. Non-drug therapies performed prior to treatment will also be included in the summary table as an additional class "non-drug therapies/surgical procedures". These therapies or procedures may not be coded by MedDRA and will be footnoted as such.

**BRACHY-CHOR-001** 

Ongoing medical diagnosis or surgical procedures will be flagged in the medical history subject-level listing.

## 3.5.6 Prior and Concomitant Therapies and Medications

#### 3.5.6.1 Prior Cancer Treatments

All prior cancer treatments will be captured regardless of time relative to being screened for the trial.

The following detailed prior chordoma therapy information will be collected:

- Any prior systemic cancer therapy (yes, no)
- Number of regimens
- Reason for administration
- Therapeutic agent
- Duration of therapy
- Best response to therapy
- Reason for discontinuation
- Field of radiation, total dose of radiation if applicable

If applicable, therapeutic agents will be coded using the World Health Organization (WHO) Drug Dictionary B3 Global version March 2018 (or higher). Frequencies of subjects who received prior cancer treatment will be summarized by Anatomic-Therapeutic-Chemical (ATC) drug class and preferred drug name. Other detailed prior chordoma therapy information will be provided in subject-level listings.

#### 3.5.6.2 Prior and Concomitant Medication

In this trial, all non-cancer treatment prior and concomitant medications taken in the 90 days prior to the screening visit will be captured. Prior medications are defined as those medications started prior to the date of first vaccination with trial product. Concomitant medications include those that are started prior to first vaccination and are ongoing at the time of first vaccination, or those that start after first vaccination. Medications can be classified as both prior and concomitant.

Other cancer therapies started after trial treatment (if allowed per protocol) will be captured on the concomitant medications page.

All prior and concomitant medications will be coded using the WHO Drug Dictionary B3 Global version March 2018 (or higher).

**BRACHY-CHOR-001** 

The incidence of prior and concomitant medication usage will be summarized separately by ATC drug class and preferred drug name, sorted by descending incidence of drug class and descending incidence of preferred drug names within drug class. A separate table will summarize prior and concomitant medication separately by preferred drug name sorted by descending frequency.

### 3.5.6.3 Non-Drug Therapies

Non-drug therapies taking place after the start of treatment will be coded to MedDRA version 21.0 or higher SOCs and PTs. These will be summarized separately from the medications and will be sorted by descending frequency of SOC, and then PT within SOC.

## 3.5.7 Treatment Exposure and Compliance

MVA-BN-Brachyury will be given subcutaneously (SC) for one dose each on Day 0 and Day 14. One dose = four 0.5 mL injections for a total dose of at least  $5 \times 10^7 \text{ Inf.U}$ .

FPV-Brachyury will be given SC on Day 28 visit, then every 4 weeks for 4 doses (End of Radiation + 2, 6, 10, and 14 weeks), then given every 12 weeks (End of Radiation + 26, 38, 50, 62, 74, 86, 98, and 110 weeks). One dose = one 0.5 mL injection with a nominal titer of 1 x  $10^9$  Inf.U per 0.5 mL.

All summaries of treatment exposure will be based on the FAS. The total number of MVA-BN-Brachyury injections will be summarized categorically as 0 - < 4, 4 - < 8, 8, and > 8. The total number of FPV-Brachyury doses will be summarized numerically and categorically as 0 - < 4, 4 - < 8, 8 - 12, and > 12. Total duration of exposure in weeks is defined as (date of last trial vaccination - date of first trial vaccination + 1) / 7. Duration of exposure will be summarized descriptively.

For radiation therapy, the percentage of subjects with different numbers of target lesions treated and non-target lesions treated (e.g., 1, 2, 3, 4 etc.) will be summarized separately. Summaries for radiation type (external beam, intensity-modulated radiation therapy [IMRT], photon beam, proton beam, stereotactic radiosurgery [SRS]), total radiation dose (Gy), and total number of fractions delivered will be summarized based on N = total number of target lesions treated or N = total number of non-target lesions treated.

All exposure data will also be provided in subject-level listings.

#### 3.5.8 Safety Analyses

All safety analyses will be based on the FAS.

### 3.5.8.1 Safety Variables

**TEAEs** 

BRACHY-CHOR-001

TEAEs to be analyzed include Grade 3 (Severe) or above TEAEs, related TEAEs, and TEAEs that lead to discontinuation of trial product.

#### **SAEs**

AESIs (immune-mediated AE)

#### Injection site reactions events

Immunotherapy Toxicity Events (Tsimberidou et al., 2018)

## **Physical Examinations**

Physical examinations or targeted physical examinations will be performed at screening and every visit during the trial. Any findings occurring after the signing of informed consent will be reported as baseline signs and symptoms on the AE form, and any findings discovered after start of trial treatment through the end of the trial will be reported as adverse events.

